12.3.4 Managing a participant who develops clinical signs of TB

Clinical suspicion of TB is defined as:

Objective evidence of TB (cough, fever, night sweats, weight loss, or

hemoptysis) based on history and/or physical examination **PLUS** radiographic findings, and without concurrent illness that would explain the findings.

Sputum Acid Fast Bacilli Smear, Gene Xpert, and Sputum Culture X 2 Whenever active TB is suspected, Gene Xpert, sputum AFB smear and sputum culture X 2 should be performed. Positive cultures should undergo speciation, and drug susceptibility testing if positive for MTB. A regional or central reference laboratory may be used.

12.3.5 Managing a participant who requests premature discontinuation from study treatment

A participant may request premature discontinuation from study treatment. A post early termination visit should be performed in 14 days to assess for any late-onset adverse events.

The participant should continue to be followed in the study per the study schedule, unless the participant withdraws consent. The participant should be referred to appropriate local sources of care for management of tuberculosis.

12.3.6 Managing a participant who is incarcerated after enrollment

This study will not enroll prisoners. However, it is possible that a participant could become incarcerated after enrollment. If an enrolled individual is incarcerated, then study medications will be stopped and the participant will be treated with TPT according to the standards of the institution in which s/he is incarcerated.

While incarcerated, individuals will not be followed in the study. When the individual is no longer incarcerated, study treatment and/or study follow-up may continue at the discretion of the investigator, if timing is within the window of all other protocol criteria.

12.3.7 Post Early Termination Visit (Visit after Early Termination) for Participants Terminating before Completion of their Assigned Study Treatment

The early termination visit should occur 14 days (+/- 3 days) after stopping study drugs, in order to assess for late manifesting adverse events.

The following should be performed:

- Review contact information
- Symptom assessment
- Adverse event assessment

• Concomitant medication assessment

Participants experiencing an adverse event at the time of early termination should be followed until resolution or stabilization of the event.

Participants who were receiving study treatment at the time of early termination will be referred to local sources for tuberculosis care.

For study purposes, such participants should continue to be followed in the study for outcome determination in accordance with the study MOOP, unless the participant withdraws consent.

A participant who withdraws consent will not have follow-up study procedures.

12.3.8 Missed Visit

A visit is classified as missed if it does not occur within the defined visit window of +/-3 days from the scheduled visit.Register as unscheduled visit, detailed below.

12.3.9 Unscheduled Visit

An unscheduled visit refers to a protocol-required study evaluation that does not occur within the defined visit window.

During an unscheduled visit, all procedures described in the protocol for the particular missed visit should be completed, including a study visit that occur solely because of an adverse event or a possible poor treatment response.

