11.1.4 Assessment of Participant Adherence with Study Product(s)/Intervention(s)

Prior to treatment initiation, each participant will receive treatment adherence counselling which will include information regarding the treatment, side effects, assistance with methods for remembering to take the medication, and discussion of any anticipated problems with taking medication. At each study visit, participants will be reminded to take all their medication. HP will be taken as self-administered therapy (SAT) in both treatment arms.

In both arms, the study team will use several measures to monitor treatment completion, including:

- Participants will maintain a medication diary for SAT
- Self-reported dosing at each monitoring visit
- Pill counts. Participants will bring their unused study medication with them. Study staff will count the remaining pills to estimate the number of scheduled doses taken
- Pharmacologic monitoring:

Isoniazid urine testing. The Isoscreen (GFC Diagnostics) point-of-care test, a colorimetric test based on the Arkansas method, (Guerra) will be used according to manufacturer-recommended methods that we have previously validated in Brazil. (Kendall) In the presence of isoniazid metabolites, this test causes urine to change color from yellow to green to indicate low levels detected or to blue-black to indicate high levels detected; urine remains yellow with no visible color change at five minutes if no isoniazid metabolites are detected. The sensitivity of any positive result has been estimated as 95-99% at 24 hours and 85% (95% binomial confidence interval 76-91%) at 48 hours after the last dose of 300mg of isoniazid. The sensitivity of a strongly positive result is estimated to be >99% at 12 hours, 68-82% at 24 hours, and 5% at 48 hours. Results are negative 72 hours after the last dose in 87% (78-92%) of patients. (Kendall)

Tests will be performed by laboratory technicians at each site but not shared with study staff or patients, as the test is not FDA-approved and cannot be used for clinical management.

Instructions for specimen collection and processing will be included in the study's Manual of Operations. (http://www.gfcdiagnostics.com/isoscreenprocedures.html)

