Rifapentine concentrations in dried blood spots (DBS). Rifapentine has a half-life of 14-16 hours and its des-acetyl metabolite has a Tmax of 24 hours. (Dooley, 2012) At the dosages proposed for this trial, detectable levels of both rifapentine (RPT) and des-acetyl rifapentine (des-RPT) can be detected in whole blood and plasma for up to 50 hours. Investigators at

the Johns Hopkins Clinical Pharmacology Analytic Laboratory (CPAL) have validated the accuracy and robustness of DBS measurement of RPT and des-RPT. (Parsons) They compared plasma and whole blood-DBS levels from healthy volunteers and found acceptable inter-subject variability. The mean concentration and lower limit of quantification for RPT were 2644 ng/ml and 53.5 ng/ml for DBS and 2475 ng/ml and 56.6 ng/ml for plasma. Results were reliable after 11 weeks of storage at room temperature without light.

We will collect whole blood by venipuncture in EDTA tubes and spot 25ul on Whatman protein saver 903 cards. After air-drying, cards will be stored at ambient temperature in plastic bags away from light. Batches of cards will be shipped to Johns Hopkins quarterly and stored at the CPAL. RPT and des-RPT analyses will be performed in batches. A 6 mm spot will be punched using a Perkin-Elmer DBS puncher and placed in a 96 deep-well plate. An extraction solvent of 90:10 methanol-to-50 mM ammonium formate buffer ratio with 0.5 mg/ml ascorbic acid will be added and the plates will be capped and mixed on a titer plate shaker for 1 h. Aliquots of 400 ul will be withdrawn and analyzed by LC-MS/MS, as previously described. (Parsons)

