- urine pregnancy test for participants of childbearing potential

Week 24 (+/- 3 days)

The study team will conduct the following assessments:

- -TB symptom screen
- targeted physical exam
- adverse event assessment
- urine pregnancy test for participants of childbearing potential
- patient costing survey

This is the final study visit
Arm B: Rifapentine 900 mg once-weekly and isoniazid 900 mg once- weekly for 12 weeks (3HP)

Arm B will have 250 participants.

Weeks 0-4

All once-weekly doses of rifapentine/isoniazid (HP) will be self-administered at home by the participant, except for the initial dose which will be supervised by the study staff in clinic. Participants will record their HP dose taking and dose-related food intake/time on a medication diary card (Appendix II).

The research pharmacy at each site will dispense 4 rifapentine blister packs, each with 8 tablets (1.33 doses per pack, 5.33 doses total) and 12 or 15 300 mg INH tablets to cover the visit window period. An extra dose of medication will be provide to allow for vomited doses and to reduce the likelihood of medication dumping. Participants will be told to bring unused medication back to clinic for the 2, 4, 8 and 12 week visits.

At enrolment, 50 participants will be selected to complete the patient costing survey and be asked to complete this same survey two additional times during their follow visits (at completion of treatment and at the end of the study participation)

Week 2 (+/- 3 days)

The study team will conduct the following assessments:

- TB symptom screen
- targeted physical exam
- adverse event assessment
- adherence questionnaire
- Pill count of HP, review of medication diary card
- CBC
- chemistry panel including liver function tests
- Urine pregnancy test for participants of childbearing potential

Week 3 (+/- 3 days for visit) Day 22 (24 hours after HP dose #4 was taken)

The participant will arrive to clinic at least an hour early, so that everything is in place for drug sampling events to begin on time.

Collect the blood and urine for drug sampling and record the exact time the sample blood and urine was collected.

The study team will conduct the following assessments:

- TB symptom screen
- targeted physical exam
- adverse event assessment
- adherence questionnaire

- pill count of returned HP, review of medication diary card

- CBC

- chemistry panel including liver function tests
- Dried blood spot and urine collection for drug sampling

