- Sampling for NAT2 gene
- urine pregnancy test for participants of childbearing potential

Week 8 (+/- 3 days)

Study team will conduct the following assessments:

- TB symptom screen
- targeted physical exam
- adverse event assessment
- adherence questionnaire
- pill count of returned HP, review of medication diary card
- CBC
- chemistry panel including liver function tests
- urine pregnancy test for participants of childbearing potential

Week 12 (+/- 3 days for visit, but not for drug sampling) Day 85 (24 hours after HP dose #12 was taken)

The participant will arrive to clinic at least an hour early, so that everything is in place for drug sampling events to begin on time.

Collect the blood and urine for drug sampling and record the exact time the sample blood and urine was collected.

The study team will conduct the following assessments:

- TB symptom screen
- targeted physical exam
- adverse event assessment
- adherence questionnaire
- patient costing survey
- pill count of returned HP, review of medication diary card
- CBC
- chemistry panel including liver function tests
- Dried blood spot and urine collection for drug sampling
- urine pregnancy test for participants of childbearing potential

This is the final dose for the 3HP regimen.

Week 16 (+/- 3 days)

The study team will conduct the following assessments:

- TB symptom screen
- targeted physical exam
- adverse event assessment

- urine pregnancy test for participants of childbearing potential

Week 24 (+/- 3 days)

The study team will conduct the following assessments:

- TB symptom screen
- targeted physical exam
- adverse event assessment
- urine pregnancy test for participants of childbearing potential
- patient costing survey

This is the final study visit.

12.1.5 Treatment completion and successful treatment.

1HP

Completion of therapy is defined as having completed 28 daily doses of treatment within 6 weeks. Treatment success is defined as having taken at least 25 doses of medication confirmed by patient report and pill count, and having rifapentine or isoniazid detected in urine or DBS specimens.

3HP

Completion of therapy is defined as having completed at least 12 weekly doses of treatment within 18 weeks. Treatment success is defined as having taken at least 11 doses of medication confirmed by patient report and pill count, and having rifapentine or isoniazid detected in urine and DBS specimens.

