10.2 Outcome Definitions

10.2.1 Treatment completion and successful treatment

1HP

Completion of therapy is defined as having completed 28 daily doses of treatment within 6 weeks. Treatment success is defined as having taken at least 25 doses of medication confirmed by patient report and pill count, and having rifapentine or isoniazid detected at least once in urine or DBS specimens.

3HP

Completion of therapy is defined as having completed at least 12 weekly doses of treatment within 18 weeks. Treatment success is defined as having taken at least 11 doses of medication confirmed by patient report and pill count, and having rifapentine or isoniazid detected at least once in urine or DBS specimens.

Figure 2 shows the algorithm that will be used to classify patients as having treatment success of failure. This hierarchical approach begins with self-reported adherence, then uses pill count, and finally a composite of test results for isoniazid in urine and rifapentine and des-RPT in DBS.

[figure not shown]

Figure 2 Treatment Success

For the treatment success outcome, note that when loss to follow up precludes being able to demonstrate the requisite number of doses having been taken, the outcome is classified as "unsuccessful." A sensitivity analysis will be conducted among those who complete their last scheduled visit after 23 weeks on study.

10.2.2 Safety: Numbers of participants with at least one occurrence of Grade 2 or higher targeted safety events and/or discontinuation of study medications because of side effects attributed to study medications.

Targeted safety events are hypersensitivity syndrome, rash, peripheral neuropathy, hepatotoxicity, nausea and vomiting, and drug-related fever.

This study will grade toxicity and adverse events according to the *Division of AIDS (DAIDS) Table for Grading Adult and Pediatric Adverse Events, Corrected Version 2.1* (dated July 2017).

https://rsc.niaid.nih.gov/sites/default/files/daidsgradingcorrectedv21.pdf See Appendix V of the study protocol.

For the primary safety outcome as of 24 weeks, those who do not complete their last scheduled visit after 23 weeks on study will be considered as failures (safety events).

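### The catch-up rule for missed visits does not say how drug samples are re-timed to a dose, so adherent participants late at both sampling visits can fail primary outcome 1, mainly in the 3HP arm

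*Protocol*

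**What the plan says.** **Missed visits.** Protocol 12.3.8: "A visit is classified as missed if it does not occur within the defined visit window of +/-3 days from the scheduled visit". Such a visit is recorded as unscheduled, and 12.3.9 adds: "During an unscheduled visit, all procedures described in the protocol for the particular missed visit should be completed".

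**Sampling times.** Protocol 12.1.4 ties both Arm B drug samples to a dose. The first is headed "Week 3 (+/- 3 days for visit) Day 22 (24 hours after HP dose #4 was taken" and the second "Week 12 (+/- 3 days for visit, but not for drug sampling) Day 85 (24 hours after HP dose #12 was taken". Arm A is sampled at Weeks 2 and 4, before that day's dose and so about 24 h after the previous one. Arm A's last dose is taken at the Week 4 visit.

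**Detection limits.** Protocol 11.1.4 says that rifapentine and its metabolite "can be detected in whole blood and plasma for up to 50 hours". For the urine isoniazid test after 300 mg it gives 95-99% sensitivity at 24 h and 85% at 48 h, and then: "Results are negative 72 hours after the last dose in 87% (78-92%) of patients".

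**Use in the outcome.** In both arms, SAP 10.2.1 requires enough doses by self-report and pill count, together with "having rifapentine or isoniazid detected at least once in urine or DBS specimens".

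**The concern.** Whether a sample is positive depends on adherence and on the time since the last dose. Under daily dosing a late visit hardly changes that interval while treatment continues. Under weekly dosing it usually moves the sample outside the detection range. The protocol recognises this at Week 12, where it withholds the visit window from drug sampling, but 12.3.9 does not carry that protection to catch-up visits. By the time a visit counts as missed, the 24 h point after dose 4 or dose 12 has passed, and no substitute is named.

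At stake is the treatment-success comparison. Someone who took the doses but attended late could be classified as unsuccessful, more often on 3HP than on 1HP. That error runs in the direction of the superiority hypothesis.

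**Working it through.** **The plan's own figure.** With 80% v 90%, household size m = 2, CV k = 0.15 and two-sided 0.05, households per arm = 1 + (1.960 + 0.842)² × [(0.16 + 0.09)/2 + 0.15² × (0.64 + 0.81)] / 0.10² = 124.7. That is 125 households, or 250 participants per arm, as stated in Protocol 15.4. The sample size is not in question; 250 per arm is used below.

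**3HP, first sample.** Doses fall on Days 0, 7, 14, 21, 28 and so on, with the visit due on Day 22. The window ends on Day 25, so a catch-up falls on Day 26 or later. Rifapentine is taken as detected up to 50 h and not after; the isoniazid test is 13% positive at 72 h (100% − 87%) and assumed 0 from 96 h.

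| Day | Hours since last dose | Chance either drug is detected |
|---|---|---|
| 26 | 120 | 0 |
| 27 | 144 | 0 |
| 28 (before dose) | 168 | 0 |
| 29 | 24 | about 1 |
| 30 | 48 | about 1 |
| 31 | 72 | 0.13 |
| 32 | 96 | 0 |

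By whole days, the average is (1 + 1 + 0.13)/7 = 30%. By uniform arrival over the week, rifapentine alone gives 50/168 = 30%. Adding isoniazid, interpolated linearly between the documented points and down to 0 at 96 h, adds about 11.7 h, giving 61.7/168 = 37%. A late first sample is therefore uninformative about 63-70% of the time.

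**3HP, second sample.** It is due 24 h after dose 12, and no dose follows. More than 3 days late means at least 24 + 96 = 120 h after that dose, which is beyond both limits unless dose 12 was itself delayed.

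**1HP.** A late Week 2 visit (Day 18 or later) still falls within daily dosing, about 24 h after a dose, and is informative. A late Week 4 visit (Day 32 or later) is at least (32 − 28) × 24 = 96 h after a Day 28 dose. It is uninformative unless doses were delayed or spare doses used.

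**False failure in 3HP under the SAP rule.** Both samples must be negative, so f = P(late at both visits) × 0.70 × 1. The documents give no lateness rate; L is an assumed rate per visit.

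| L | f if independent (L² × 0.70) | f if the same people are late twice (L × 0.70) |
|---|---|---|
| 5% | 0.2% | 3.5% |
| 10% | 0.7% | 7% |
| 20% | 2.8% | 14% |

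With 0.63 in place of 0.70, the independent column becomes 0.16%, 0.63% and 2.5%. For 1HP, f is near 0, because the Week 2 sample satisfies the criterion even when late.

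**Effect on the test.** Take true success as 90% in both arms, so that observed 3HP success is 0.90 × (1 − f). Rejection in favour of 1HP is found by exact enumeration of Fisher's test at two-sided 0.05, 250 per arm, participants independent.

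| f | Observed 3HP success | Chance of declaring 1HP superior |
|---|---|---|
| 0 | 90.0% | 1.8% |
| 0.2% | 89.8% | 2.1% |
| 0.7% | 89.4% | 3.1% |
| 2.8% | 87.5% | 11% |

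The bias in the risk difference is 0.9f: about 0.2, 0.6 and 2.5 percentage points. At the fully correlated limits of 3.5%, 7% and 14%, the same enumeration gives about 16%, 50% and 96%. Those are upper bounds for each assumed L.

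**The case against.** **12.3.9 already carries the timing over.** It refers to the procedures described for the missed visit, and for Arm B these are samples 24 h after a named dose. A reader might infer that staff are told to sample whenever the participant arrives; the text does not say that. This much stands: the fault is silence, not a wrong instruction. But the named doses are already more than 24 h past, so the rule cannot be followed literally.

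**The problem is not confined to 3HP.** A late Week 4 sample in 1HP is also past detection. Protocol 12.1.5 and 15.2.1 word the assay criterion differently from the SAP. Section 15.2.1 asks for detection in urine and DBS in both arms, without saying that once is enough. If every visit's specimens had to be positive, late 1HP participants could fail too. This stands. The near-complete asymmetry belongs to the SAP rule.

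**One late visit is not enough.** Under the SAP, one well-timed positive sample protects the participant. This also stands.

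**The size rests on assumed lateness.** Protocol 10.3 provides reminder calls, calls after missed visits and home visits, so rates may be low. At 5-10% independent lateness the effect is small. Against that, lateness tends to recur in the same person, which pushes f towards the right-hand column.

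**Rules may exist elsewhere.** Figure 2, which classifies success, is not shown, and Protocol 11.1.4 leaves specimen instructions to the Manual of Operations. The claim therefore covers only the visible text. The isoniazid figures are for 300 mg, and none are given for the 900 mg weekly dose.

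**Conclusion.** The concern holds as a gap with a predictable direction. The protocol has no re-timing rule for catch-up samples, and the visible SAP text has none for counting mistimed ones. With the documents' detection limits and the SAP criterion, adherent participants late at both sampling visits can be misclassified, mainly in 3HP and in favour of 1HP. The effect is slight at 5-10% independent lateness (2.1-3.1% against 1.8%), and material at 20% (11%) or where the same people are late twice. These figures assume on-schedule dosing, independent participants and equal true success of 90%.

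The documents do not support three stronger conclusions: that only control participants can be affected, that a single late visit causes failure under the SAP, or that a large inflation of the superiority claim is established.

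A separate conflict interacts with this one. Table 1B in Appendix I places dose 1 at week 0 and the second sampling visit at week 11, so an on-schedule dose 12 falls near Day 77. Section 12.1.4 labels Day 85 as 24 h after dose 12, yet it would be (85 − 77) × 24 = 192 h after an on-schedule dose. If the second sample is uninformative even when on time, one late Week 3 visit could suffice, and f becomes L × 0.70. The catch-up rule does not cause this conflict, but the passages must be reconciled.

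**What to change.** 1. **Protocol 12.3.9.** State that an Arm B catch-up visit that includes drug sampling is booked at the protocol's own interval of 24 h after the next self-administered weekly dose, while doses remain. State also that the other procedures of the visit need not wait. Staff already telephone to rebook missed visits.
2. **SAP 10.2.1.** Keep the primary success rule unchanged. In both arms, flag any sample drawn more than about 50 h after the last recorded dose; the diary and the recorded collection times supply the interval. Prespecify two sensitivity analyses for participants with no well-timed sample: classify them on self-report and pill count, then as failures. A flag is preferable to excluding such samples from the primary rule. Dose times come from the participant's diary, so exclusion would let self-report decide whether the objective check applies, and would leave some participants unclassified.
3. **Protocol 12.1.4 and Table 1B.** Reconcile the day given for dose 12 and its sample.

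The cost is a few sentences, a few Arm B sampling days moved and slightly more analysis. No re-timing can rescue a late sample after dose 12; the flag and the sensitivity analyses cover that case.

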12.3.10 Final Study Visit

The final study visit is at week 24, for TB symptom screen, AE assessment, and targeted physical exam.

